### **4.2 Hypotheses:**

People with Parkinson's Disease with dysphagia who participate in a four-week intervention using ultrasound visual feedback and principles of motor learning will show improvements in their swallowing efficiency (i.e., reduction in time taken to swallow liquid and food)

### 6. STUDY DESIGN

#### 6.1 Type of Study

[figure not shown]
This is a Single Case Experimental Design with multiple baselines within participant study

#### 6.2 Schedule of Events/ Treatment Phases

Table 1 study timeline (subject to approval timeframe)

Events and Time		
September - October 2024	November 2024- September 2026	October 2026
Ethics, Clinical trial registration	Rolling recruitment, assessment and therapy	Close Trial

#### Schedule for individual participants from recruitment to follow-up:

**Tasks and Data Collected during Assessment and Probes:**

TIMING	Screener	Assessment	Phase: A1 Baseline Pre-treatment Baseline Probes	Phase: B Treatment Probes	Phase: A2 Baseline post-treatment		Phase C: Four week follow up
					Post-treatment Assessment	Maintenance Probes	
TASKS		1-2 visits	three times weekly across baseline period	1st and 3rd therapy session each week,	same day as the 1st maintenance probe	three times weekly across the baseline period	once, 4 weeks after the last therapy session
Screening (Questionnaire of demographic Information and inclusion/exclusion criteria)	X						
Timed Water Swallow Test (Hughes & Wiles, 1996; Sarve et al., 2021) (Video Recording)		X	X	X	X	X	X
Test of Mastication and Swallowing Solids (Athukorala et al., 2014; Huckabee et al., 2018) (Video Recording)		X	X	X	X	X	X
Information regarding time taken to complete meal and IDDSI Level (Cichero et al., 2017) (Images of food, Questionnaire)		X	X	X	X	X	X
Clinical Swallow Evaluation with Ultrasound using the MBSImp Rating Scale (Martin-Harris et al., 2008) for oral phase components (Video recording)		X	X	X	X	X	X

Swallowing Quality of Life Questionnaire (SWAL-QoL) (Questionnaire) (McHorney et al., 2002)		X				X		X
Theoretical Framework of Acceptability Questionnaire (Sekhon, Cartwright & Francis, 2022) (Questionnaire)						X		
Maximum Phonation Time (MPT) (Speyer et al., 2010) (Audio Recording)		X	X	X	X	X	X	X
Swallowing Disturbance Questionnaire (SDQ-PD) (Manor et al., 2007) (Questionnaire)	X					X		X
30 second monologue (Audio Recording)		X	X	X	X	X	X	X
North Wind and the Sun passage (Amundsen & Hansen, 2014) (Audio Recording)		X				X		X
Picture description (Audio Recording)		X				X		X
Rate at which participants can accurately repeat a series of rapid, alternating sounds as per published normative data (Kent, Kim & Chen, 2022) (Video Recording)		X	X	X	X	X	X	X

## **PROCEDURES**

### **Recruitment**

Participants will be recruited from The University of Sydney speech pathology clinic (The SPEECH Clinic), speech-language pathology services in Sydney and the public. The study will be advertised on the researchers' social media accounts (Instagram, Facebook, LinkedIn and Twitter/X) the University of Sydney SPEECH Clinic Facebook page, Speech Pathology Australia e-newsletter and website, and the University of Sydney research participation page. The study advertisement will also be sent to Parkinson's Disease support groups, Parkinson's Disease advocacy groups (e.g., Parkinson's Australia, Parkinson's NSW), Parkinson's Disease clinics, Parkinson's Disease research teams as well as neurologists and speech pathologists working with PwPD in New South Wales. Contact details of the support groups, advocacy groups, clinics, research teams and clinicians are publicly available.

The study advertisements will direct potential participants who are interested to contact the PhD student ([name] M) for further information or express their interest through a survey on the REDCap secure platform. When participants contact the PhD student, they will be informed about the purpose of the study and provided with the Participant Information Sheet. An opportunity to ask questions will be provided.

### **Expression of Interest in the Study**

Those interested in the study will be asked to contact the PhD student or follow links from social media or study advertisements to express their interest on a REDCap form. Potential participants will be provided with the Participant Information Sheet and participant consent form for the screener.

### **Screener:**

As part of the screening process, participants will answer questions pertaining to the inclusion and exclusion criteria to determine their eligibility for the study. This process should take ~30 minutes and will be completed over the phone. If potentially eligible for the study, potential participants will be invited to enrol in the study and undergo the next steps in the informed consent process.

### **Informed Consent to Participate:**

As part of the informed consent process, the PhD student will go through the information on the Participant Information Sheet and the Participant Consent Form with the participant. Participants will be encouraged to ask questions about the research and the risks and benefits of participation. Potential participants will be informed that their participation is completely voluntary. They are free to decline to attend the study, and free to withdraw from the study at any time. This will have no implications on their relationship with the research team or the University of Sydney. Consent will be recorded in (1) a RedCAP version of the participant consent form or (2) a written consent form which will then be scanned and added to RedCAP.

### **Allocation to Baseline Phase:**

Once enrolled in the study, participants will be randomly allocated to varying baseline duration through a computer-generated block randomisation.

## Assessment

Following screening and consent, participants will be assessed by a qualified speech pathologist (one of the investigators) using standard speech pathology tools. As shown on page 8, the assessment will include the (a) Timed Water Swallow Test (TWST) (Hughes & Wiles, 1996; Sarve et al., 2021), (b) Test of Masticating and Swallowing Solids (TOMASS) (Athukorala et al., 2014; Huckabee et al., 2018), (c) a clinical swallow trial with the ultrasound to determine severity of oral phase deficits based on a checklist based on components 2, 3, 4 and 5 of the Modified Barium Swallow Impairment Profile (MBSImp) (Martin-Harris et al., 2008) (d) questions about the type of modification they need for the meal based on the The International Dysphagia Diet Standardisation Initiative Level (IDDSI) (Cichero et al., 2017), (e) the time taken to complete meals, and the (f) Swallowing Quality of Life Questionnaire (SWAL-QoL) (McHorney et al., 2002).

Control measures including the (a) Maximum Phonation Time, (b) Speech Rate (Syllables per minute during a 30 second monologue), (c) Average decibel in 30 second monologue and (d) Percent Intelligibility Rating based on Frenchay-2 Rating scale (perceptual) (Enderby & Palmer, 2008) will be recorded.

The assessment will be audio and video recorded. If participants experience fatigue, the assessments will be conducted over 2 sessions.

## Treatment

Treatment will be provided by a trained speech pathologist with more than 5 years of experience following the training schedule at a mutually convenient time. Treatment will consist of swallowing liquids or solids with ultrasound biofeedback on the tongue movement pattern during swallowing. Each visit will take approximately 45-60 minutes and involve up to 50 swallows (either fluid, food, or saliva swallows). Treatment sessions will be recorded for fidelity checking. No home practice is required.

## Probes

As shown on page 8, Probes for Phase A1 and A2: The TWST and TOMASS and a measurement of maximum phonation time and a 30 second monologue will be obtained 6 times for those allocated in the 2-week baseline periods and 9 times for those allocated in the 3-week baseline period.

Probes for Phase B: Treatment probes will be taken twice weekly (on the day of the first and last therapy session each week) for 4 weeks. Treatment probes will be identical to the baseline probes and will be collected immediately before therapy commences on that day.

The probes will take approximately 30-40 minutes and breaks will be provided if a participant experiences fatigue.

After the end of Phase B, a repeat assessment will be completed (identical to the one conducted at the start of the treatment program) by a qualified speech pathologist. Participants will also be asked to complete a Theoretical Framework of Acceptability Questionnaire to understand their acceptance and the feasibility of the intervention.

As this is a pilot, the frequency and duration of the treatment sessions, the duration and frequency of breaks provided, the type of foods and fluids used, the amount and type of feedback provided and the number of times the participant is asked to swallow and sets of swallows may be altered based on participants' fatigue level and response to the therapy protocol.

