### **6.3 Population/ Calculation of sample size**

Sample size calculation: This is a phase 1 study to acquire data for a sample size calculation. Considering no protocol exists for ultrasound visual feedback in dysphagia rehabilitation in people with Parkinson's, the researchers will first aim to assess the feasibility of use with a single participant. Subsequently, n=6 will be recruited to allow for attrition expected in behavioural rehabilitation. This follows a similar sample size to other pilot studies (Blyth, McCabe, Madill, & Ballard, 2017).

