#### *6.4.3 Randomisation and Blinding Processes*

As it is a behavioural study, participants and the therapist will not be blinded to the intervention. However, the assessors will be blinded to the sequence in which the probe data is collected (i.e., the assessor will review the task recordings to obtain the probe data and will not know which week a specific recording was obtained). This will be achieved by getting an independent person to re-order the recordings of sessions so that they are not chronological, and the assessors will evaluate the outcome measures without knowing if they are from the baseline or intervention phase. Participants will be randomised into different lengths and onset of baseline phase prior to assessment.

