#### *6.7.3 Replacements*

Replacements will be sought for participants who withdraw from the study to ensure a minimum data set of  $n=3$

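### The analysis in section 6.14 uses neither the randomised onset of treatment nor time, so a practice gain on the swallowing tests would be counted as treatment effect; the design label should read across participants

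*Protocol*

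**What the plan says.** - **Label.** Section 6.1: "This is a Single Case Experimental Design with multiple baselines within participant study". The Synopsis gives Part 2 the same label and the purpose of determining efficacy.
- **Allocation.** Section 6.2 (Allocation to Baseline Phase): "participants will be randomly allocated to varying baseline duration through a computer-generated block randomisation". Section 6.4.3: "Participants will be randomised into different lengths and onset of baseline phase prior to assessment". Block size and ratio are not given.
- **Probes.** The schedule table has A1 probes "three times weekly across baseline period", and A2 likewise. Section 6.2 (Probes) names two lengths, with counts of "6 times for those allocated in the 2-week baseline periods and 9 times for those allocated in the 3-week baseline period". For phase B: "Treatment probes will be taken twice weekly (on the day of the first and last therapy session each week) for 4 weeks".
- **Numbers.** Section 6.3: "Subsequently, n=6 will be recruited to allow for attrition expected in behavioural rehabilitation". Section 6.7.3: "Replacements will be sought for participants who withdraw from the study to ensure a minimum data set of" three.
- **Analysis.** Section 6.14 graphs and inspects the experimental and control measures. If change over time is seen and the repeated measures show no significant correlation, d2 is calculated within each participant. If there is serial dependency, PND is calculated against the highest A1 point. Section 6.14 mentions no baseline length, randomised onset, trend or comparison across participants.

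**The concern.** In a within-participant multiple baseline, different treated behaviours of one person enter treatment at different times. Here the Timed Water Swallow Test (TWST) and the Test of Masticating and Swallowing Solids (TOMASS) enter it together, and the speech and voice controls are never treated. The stagger exists only between people, so the label and the randomisation describe different designs.

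The stagger is what allows a treatment effect to be told from steady improvement through repetition: a practice curve follows the probe count, whereas a treatment effect follows the randomised start. Both d2 and PND compare phases inside one person, where later phases always come after more practice. The screen before them does not help, because a trend also satisfies a criterion of change over time.

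Two uses of the results are at stake: the efficacy statement for Part 2, and the sample-size calculation that section 6.3 says the study is to inform. Effect sizes inflated by practice would make the next trial too small.

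**Working it through.** **Probe counts.** 3 per week × 2 weeks = 6 and 3 × 3 = 9, as stated. Phase B: 2 × 4 = 8. Total per participant: 6 + 8 + 6 = 20 or 9 + 8 + 9 = 26, before the assessments and follow-up.

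**What the indices give when treatment does nothing.** The documents give no SD and no practice effect, so these are assumptions: linear gain of 0.05 or 0.10 SD per probe, independent normal errors, improvement scored upward, d2 taken as mean difference over pooled SD.

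Shift between phases = gain per probe × distance between phase midpoints.
- 6/8/6: midpoints at probes 3.5, 10.5 and 17.5. A2 − A1 = 14 probes, or 0.70 and 1.40 SD. B − A1 = 7 probes, or 0.35 and 0.70 SD.
- 9/8/9: midpoints at probes 5, 13.5 and 22. A2 − A1 = 17 probes, or 0.85 and 1.70 SD. B − A1 = 8.5 probes, or 0.425 and 0.85 SD.

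Simulation (100,000 series per row) gives slightly larger values of d2, because the SD is estimated from few points:

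| Probes | Gain per probe | Mean d2, A2 vs A1 | Mean d2, B vs A1 | PND in A2 |
|---|---|---|---|---|
| 6/8/6 | 0 | 0.00 | 0.00 | 14% |
| 6/8/6 | 0.05 SD | 0.76 | 0.37 | 32% |
| 6/8/6 | 0.10 SD | 1.49 | 0.73 | 54% |
| 9/8/9 | 0 | 0.00 | 0.00 | 10% |
| 9/8/9 | 0.05 SD | 0.89 | 0.44 | 29% |
| 9/8/9 | 0.10 SD | 1.72 | 0.87 | 56% |

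The rows without trend agree with theory for PND: a later point exceeds the best of n baseline points with probability 1/(n + 1), so 1/7 = 14% and 1/10 = 10%. PND therefore also depends on the allocated length. A trend set per week gives the same picture: 0.1, 0.2 and 0.3 SD per week yield mean A2-versus-A1 d2 of 0.65, 1.29 and 1.93 (2-week) or 0.73, 1.45 and 2.12 (3-week).

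**What the randomised onset could offer.** The smallest one-sided p of a randomisation test is 1 divided by the number of possible allocations.

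| Participants and scheme | Allocations | Smallest p |
|---|---|---|
| 6, one block split 3:3 | C(6,3) = 20 | 0.05 |
| 6, blocks of two | 2³ = 8 | 0.125 |
| 6, independent draws | 2⁶ = 64 | 0.016 |
| 3, at best | 2³ = 8 | 0.125 |
| 3, split 2:1 | 3 | 0.33 |

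With six participants split 3:3, a common trend of 0.2 SD per week and an abrupt level change at onset, an exact test over the 20 allocations rejected (p ≤ 0.05) in about 5% of simulations with no effect. It rejected in 35%, 81% and 98% for changes of 1, 2 and 3 SD.

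**The case against.** A reader might infer that the design itself cannot separate treatment from practice. The documents do not support that. With two randomised onsets and six participants in one 3:3 block, a test that uses the onset holds its error rate under a common trend and has reasonable power for a large abrupt change. The gap is in the stated analysis.

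A reader might also infer that the onset is ignored altogether. Visual inspection comes first in section 6.14, and staggered graphs can be read for onset, although the section does not say they will be. A separate statistical analysis plan, not seen here, could add a test. Still, section 6.14 names its indices and defers nothing.

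The protocol has other safeguards. The speech and voice controls are taken at the same probes, graphed alongside and predicted not to improve. Assessors do not know the order of the recordings. There are A2 probes and a follow-up. These stand in part: the controls address general drift, but not practice specific to drinking water and eating biscuits against the clock, and A2 cannot tell retained learning from practice.

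The size of the bias is assumed. Practice may plateau, and section 7.2.1 expects possible decline with disease progression, which would bias the indices the other way. A2 against A1 is the most distant contrast and section 6.14 does not fix it. B against A1 gives about half the bias, which is still not zero.

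Finally, a reader might think that more onset points are essential. Four possible starts drawn independently give 4⁶ = 4096 allocations, but setting that against 8 or 20 compares independent draws with blocked ones. The like-for-like figure for two lengths is 64. At six participants the gain in power is small: about 91% against 95% for a 2 SD change in one simulation.

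**Conclusion.** The point holds as a gap in the analysis together with a wrong label. As section 6.14 stands, d2 and PND would report practice on the TWST and TOMASS as effect. With no true effect and a gain of 0.05 to 0.10 SD per probe, mean d2 is 0.76 to 1.72 for A2 against A1 and 0.37 to 0.87 for B against A1, and A2 PND goes from 10-14% to 29-56%. These sizes rest on a linear trend, independent errors and a pooled-SD form of d2, none of which the documents give. The direction needs only that improvement with repetition continues across phases.

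The present design can support a cross-participant test at six participants in one 3:3 block, where p can just reach 0.05. Blocks of two stop at 0.125. At the minimum of three participants the floor is 0.125 at best, so no such test could reach 0.05. The power figures assume an abrupt effect.

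**What to change.** 1. In the Synopsis and section 6.1, describe Part 2 as a multiple baseline across participants.
2. State the block size and ratio in the documents held away from those who enrol. The possible allocations, and hence the smallest p, follow from them.
3. In section 6.14, add a cross-participant randomisation test over the baseline-length allocations possible under that block scheme. Base the test statistic on a phase effect estimated with a time term. Keep d2 and PND as descriptive measures, and name the phases each one contrasts.
4. State that if only three participants complete, the results will be reported as descriptive and without an efficacy claim.

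More than two onset points are optional. They help mainly at three participants, and the protocol would then have to define the A2 length after 7 or 8 baseline probes, since A1 and A2 now share one count.

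The cost is some rewording and a little more analysis, with no added visits or probes. If there is a practice trend, the effect estimate will be less favourable. The changes should be made before Part 2 allocation begins, because the set of possible allocations cannot be altered afterwards.

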## **8. SAFETY CONSIDERATIONS**

### **8.1 Adverse event definition, risk assessment and mitigations**

An adverse incident is a harmful, unpleasant, or undesirable response, reaction, or outcome experienced by a research participant or researcher. In the context of this study, Serious Adverse Events include choking or chest infection resulting in hospitalisation or death.

The risk of serious adverse events is no greater than if the participant does not take part in this study. Participants in this study will be medically stable and eating and drinking in the community. Additionally, there is an exclusion criteria excluding participants who have a recent serious upper respiratory tract infection, and the therapy protocol will be carried out by a qualified and experienced speech pathologist with current CPR certification.

The researcher will contact the participants one day prior to each treatment session to ask about their health and discuss postponing the session and referral to their GP if they are unwell. The researcher will also ask the participant about their health again at the beginning of each session to confirm that they are fit to continue. If there are any concerns, they will discuss postponing the session and referral to their GP or other health practitioner with the participant.

Other potential anticipated adverse events include fatigue from the intensity of the therapy protocol and feeling full or nauseous from having to eat or drink as part of the therapy. These risks will be mitigated through:

- scheduling sessions at least 2 hours after a meal and taking their medication as normal
- reminding participants to continue with their current medication regime and that it should not be impacted by this study participation
- informing participants beforehand that they will need to eat and drink during the therapy sessions.
- and regular breaks in the session

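### The first Phase B probe is taken before any therapy, so one of the eight planned treatment-phase points is really a baseline observation

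*Protocol*

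**What the plan says.** Baseline (A1) probes are scheduled "three times weekly across baseline period" in the section 6.2 table of tasks and data collected. The Probes text gives the count as "6 times for those allocated in the 2-week baseline periods and 9 times for those allocated in the 3-week baseline period".

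For the treatment phase the same text says "Treatment probes will be taken twice weekly (on the day of the first and last therapy session each week) for 4 weeks", followed by "Treatment probes will be identical to the baseline probes and will be collected immediately before therapy commences on that day". The table agrees: under its Phase B column, probes fall on the 1st and 3rd therapy session of each week.

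Section 6.14 has the measures graphed and inspected visually, with statistical analysis only if the graphs suggest change. It then uses d2 where the measurements are not serially correlated and PND where they are, with PND referred to an extreme A1 point across all phases. It does not reassign or exclude any probe.

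**The concern.** The timing rule and the phase label conflict at one point. A probe collected before the day's therapy reflects only the therapy already received. For the first session of week 1 that is none, so the observation has the same treatment status as the A1 probes but is counted and plotted on the treatment side of the phase line.

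Three uses of the data are exposed:

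- On the graph, a baseline-level point just after the phase change blurs any immediate shift, and visual inspection decides whether statistics are run at all.
- In d2, if it contrasts Phase B with A1, the point lowers the mean difference and raises the within-phase spread.
- In PND, it takes up one of eight places that therapy cannot influence.

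Section 6.3 says the study is meant to supply data for a later sample size calculation, so an understated effect would carry forward.

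**Working it through.** **Inputs from section 6.2.** A1 probes: 3 per week for 2 or 3 weeks. Phase B probes: 2 per week for 4 weeks, each before that day's therapy. The text's first and last session, read with the table's 1st and 3rd, implies three sessions a week, or 12 in all.

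**Reproducing the plan's counts.** 3 × 2 = 6 and 3 × 3 = 9, as stated. Phase B: 2 × 4 = 8 (not stated, but it follows).

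**Therapy received before each Phase B probe.** Sessions completed: 0, 2, 3, 5, 6, 8, 9, 11. One of 8 is zero: 1/8 = 12.5%.

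**Mean difference, constant shift D after the first session.** (0 + 7D)/8 = 0.875D.

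**Mean difference, gain proportional to sessions received.** The sessions sum to 44. Mean over all 8 probes: 44/8 = 5.5 (45.8% of 12). Mean over the 7 treated probes: 44/7 = 6.29 (52.4% of 12). Ratio: 5.5/6.29 = 0.875, the same dilution.

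**Standardised difference.** The protocol does not write out the d2 formula, so I assume the mean difference divided by the pooled within-phase SD. One point lying D away from the other seven adds (7/8)D² to the Phase B sum of squares. With within-phase SD 1 and 6 A1 probes there are 6 + 8 − 2 = 12 degrees of freedom, so

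expected pooled variance = 1 + 0.875D²/12.

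For D = 2: 1 + 3.5/12 = 1.292, SD 1.137, and 1.75/1.137 = 1.54. For D = 3: 1 + 7.875/12 = 1.656, SD 1.287, and 2.625/1.287 = 2.04.

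A simulation (100,000 series, independent normal data, step effect after the first session) gives medians close to these:

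| True shift | A1 = 6: as planned | A1 = 6: probe moved to A1 | A1 = 9: as planned | A1 = 9: probe moved to A1 |
|---|---|---|---|---|
| 1 SD | 0.87 | 1.03 | 0.86 | 1.02 |
| 2 SD | 1.57 | 2.04 | 1.60 | 2.04 |
| 3 SD | 2.08 | 3.08 | 2.17 | 3.06 |

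With 6 A1 probes the loss is about 16% at 1 SD (1 − 0.87/1.03), 23% at 2 SD (1 − 1.57/2.04) and 32% at 3 SD (1 − 2.08/3.08).

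**Nonoverlap.** However strong the therapy, only 7 of the 8 points can respond to it. Measured against the best A1 point, PND for Phase B is therefore limited to 7/8 = 87.5%, unless the untreated point falls beyond that value by chance. I attach no probability to that chance. A simple figure would need exchangeable observations, and section 6.14 uses PND only when the data are serially dependent.

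**The case against.** Probing before therapy is good practice. It avoids same-day practice and fatigue effects and keeps the setting close to a baseline visit. The statement that the probes are identical concerns their content, and nothing contradicts it. Both points stand: the fault is the phase label of one probe, not the timing rule.

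Section 6.14 does not say which phases d2 contrasts. The A2 phase has its own 6 or 9 probes, all after therapy, so A2 versus A1 contains no mislabelled point in its post-treatment phase. This stands and limits the reach of the point. PND, however, runs across all phases and the graphs show all phases, so Phase B is not spared.

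For PND, section 6.14 names the highest A1 value and allows counting above or below it. If falling times are counted against the highest A1 time, an untreated point would usually qualify and the ceiling largely disappears. This also stands: the 7/8 limit holds only against the best A1 value.

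A reader might go further and infer from section 8.1 that Phase B probes fall on screened, well-timed days while A1 and A2 probes do not, which would bias the comparison towards benefit. The document does not support this. Only the day-before call is tied to treatment sessions ("The researcher will contact the participants one day prior to each treatment session to ask about their health and discuss postponing the session"). The second check is to "ask the participant about their health again at the beginning of each session", and the meal gap reads "scheduling sessions at least 2 hours after a meal and taking their medication as normal", neither expressly limited to therapy. Baseline and maintenance visits are not addressed, which is silence and not exclusion. The call leads only to a discussion of postponing, and no figure allows such a bias to be sized. Tying probes to medication timing would likewise be a design preference; the protocol contains no error on that point.

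**Conclusion.** The point holds for one probe. The week 1 first-session probe is untreated but assigned to Phase B, and no rule corrects this. The 1-in-8 count follows directly from section 6.2.

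The dilution to 0.875D applies to any Phase B versus A1 mean difference, under either a step or a proportional gain. The larger loss in the standardised effect rests on a pooled SD, independent data (the condition under which section 6.14 uses d2) and a step effect. If the SD came from A1 alone, only the 12.5% dilution would remain. The 7/8 limit on nonoverlap depends on using the best A1 point as reference.

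The direction is towards no effect, so it cannot create a false benefit. In a pilot of six participants this is a modest defect, but it is worth correcting because it can be removed almost for free before any data are graphed. It is not evidence that the Phase B comparison as a whole is invalid, nor that visit conditions favour the treatment phase.

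**What to change.** State in section 6.2 (Probes) and section 6.14 that the probe collected before the first therapy session is the last A1 observation. A1 then has 6 + 1 = 7 or 9 + 1 = 10 points, and Phase B has 8 − 1 = 7. Draw the phase line after that probe on every graph, and use the same assignment in every d2 and PND calculation. Leave the collection of probes before therapy unchanged.

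The cost is one coding rule, with no extra visits or measurements. The small downside is that this last A1 point is collected on a treatment-session day, which carries the day-before health call in section 8.1; the protocol states no such call for the other A1 visits. The rule should be fixed before any series is plotted, because moving a point between phases afterwards could look driven by the result.
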